Protocol version: 1

Date updated: 1/03/24

Reopening Schools Safely and Educating Youth (ROSSEY): Early Learning Ancillary Study

Investigator List	
Principal PI: [name] Department of Health Systems and Population Health University of Washington (UW) Hans Rosling Center for Population Health [name] [contact] [contact]	Co-Investigator: [name], MS UW Medicine/Family Medicine University of Washington [contact] [contact]
Site PI/Co-Investigator: [name], Pharm D, PhD Division of Public Health Sciences Fred Hutchinson Cancer Research Center [name] [contact]	Co-Investigator/Biostatistician: [name] Seattle Children's Hospital/ Department of Health Systems and Population Health [name] [contact] [contact]
Co-Investigator: [name] College of Health and Human Services Purdue University [name] [contact]	Co-Investigator: [name] Department of Health Systems and Population Health University of Washington (UW) Hans Rosling Center for Population Health [name] [contact]
Co-Investigator: [name], MPH Department of Global Health Hans Rosling Center for Population Health [name] [contact] [contact]	

Funding: National Institute of Child Health and Human Development

Role of funders: The funders had a role in the design of this study.

I. Study Design

This ancillary study incorporates one primary aim which is meant to help students return to school safely by providing free health education to families and their children. Simultaneously, free COVID-19 testing will be offered to families for their children at schools through the Yakima School District. We want to learn if health education can increase the uptake of COVID-19 mitigation measures, improve children's school attendance, and increase families' physical and mental well-being using single-arm pre/post-study.

The ancillary study runs parallel with the larger ROSSEY RCT. Recruitment, enrollment, and baseline assessment are expected to last two months (September-November 2022). Enrolled participants will not receive the comic book and parent video series until after completion of the ROSSEY RCT Post 1 follow-up Survey to not bias the data of older siblings participating in the ROSSEY RCT. A follow-up assessment for Early Learning participants is anticipated to take place 10 months after the launch of recruitment (July-August 2023)

II. Aim 1

Evaluate if risk communication health education can increase uptake of COVID-19 mitigation measures, improve children's school attendance, and increase families' physical and mental well-being using a single-arm pre/post study.

III. Study Population

We will collaborate with the Yakima School District to recruit Early Learning students (3, 4 and 5 years old) and their parent or Guardian(s) into the research study. We will recruit Early Learning students into the study regardless of their participation in SARS-CoV-2 testing provided by the Yakima School District. This will allow us to evaluate the effect of the risk communication strategies on the uptake of SARS-CoV-2 testing and other mitigation measures.

IV. Sample Size

Early Learning is an ancillary study with no defined sample size. We will enroll and recruit participants for a total of eight weeks.

V. Enrollment Criteria

Parent/Guardian eligibility criteria for participation in the study include:

- Must have a child attending the Early Learning Program in the Yakima School District
- Must be able to provide informed consent and legal guardian assent either virtually, on the telephone, or in-person.
- Must have a permanent mailing address available for study staff to mail necessary materials OR a working email address.

VI. Study Procedures

Recruitment, Screening and Consent

Enrollment and recruitment of the Early Learning ancillary study will start the second academic year of the RCT (2022-2023). Study information in the form of a flyer will be sent home with students to parents through school email by the principal and posted on the school Parent Square site in September of 2022. In addition, ROSSEY staff will attend the Early Learning Open House to hand out study information and obtain the phone number or email address of interested parents. ROSSEY staff will follow up with interested parents and provide further information about the study.

Families will have two options to enroll children in the study: online through a website portal (Project REDCap), or with assistance from study staff over the phone.

- Parents/guardians who choose to enroll children in the study online will provide informed consent by reading and e-signing consent and assent forms through a web-based REDCap portal, and then the participant's parent/legal guardian will complete a baseline survey (same enrollment and secondary outcomes survey from the RCT of the main study).
- Parents/guardians who choose to enroll with staff assistance over the phone will be verbally guided through the REDCap consent/assent forms, enrollment questionnaire and secondary outcomes questionnaire.

[figure not shown]
Parents who choose online enrollment will be screened for eligibility via the REDCap web-based portal. Parents who choose enrollment with staff assistance will be screened over the telephone. The online consent portal will encourage parents/legal guardians to contact research staff by phone or email to review the risks and benefits of study participation, or to review the study procedures outlined in the consent form. Since all children are under the age of 7, the parent or legal guardian will sign the consent form, and the child will provide verbal assent if able. Electronic copies of the e-signed consent and assent documents will be automatically emailed to participants. For those who enrolled by telephone, copies of the consent and assent documents will be sent to the participants either via e-mail, through the mail, or in person.

NEEDS A SECTION ON BASELINE SURVEY.

After enrollment is complete, parents/guardians of study participants will take part in the following study procedures:

Risk Communication: Risk communication, in the form of comic books with accompanying read-along videos for the children (n=3) and videos for the parents (n=2) will be distributed in English and Spanish to all enrolled students within two weeks of completion of the ROSSEY RCT final assessment (December 2023). Three comic books will be distributed by mail and parents will be sent a password-protected link with the mailed comic to access the parent videos and comic book read-along videos. All intervention materials (i.e., children's comic books and parent videos) will be distributed after the final assessment of the larger ROSSEY RCT study is complete. The delay is to eliminate possible contamination of the RCT by siblings of comparison students who will receive the comic books as part of this ancillary study.

Outline of Early Learning Study Procedures

Follow-up Survey: We will contact parents 6 weeks after the risk communication intervention distribution. Parents will be asked to complete the follow-up survey either online or by phone. The surveys will ask for updates to their contact and demographic information, child's COVID-19 vaccination status, and child's SARS-CoV-2 mitigation behaviors and the secondary outcome measures.

Following the protocol from the ROSSEY RCT, the post assessment will take place over 6 weeks, allowing two weeks for final contact prior to closure. For EL participants with missing or phone numbers no longer in service, ROSSEY staff will contact the YSD to 1) determine if the student is still attending YSD, 2) find out school and teachers name to send a notice through the school to the parent letting them know we are trying to reach them. Students determined to still be enrolled at YSD, and are non-responders to the follow up survey, will receive an at home visit by ROSSEY staff as a final attempt to reach student and parent to complete survey. Follow-up assessment closure will take place one week after completion of home visits.

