ReOpening Schools Safely and Educating Youth (ROSSEY Study) – Early Learning Ancillary Study

Clinical Trials.gov : NCT05965323

June 30, 2022

STATISTICAL ANALYSIS PLAN

1. Introduction to the SAP

This statistical analysis plan (SAP) describes the plans for statistical analyses that will address the study's protocol objectives.

2. Study Schema and objectives

Purpose:	Evaluate if risk communication health education can increase uptake of COVID-19 mitigation measures, improve children's school attendance, and increase families' physical and mental well-being using a single-arm pre/post study.
Design:	A single-arm pre/post-study
Central Hypotheses:	Our central hypotheses are that students and parents who view the risk communications will be more likely to have increased COVID-19 testing and vaccine uptake.
Primary Objectives:	
• To determine if implementing three COVID-19 education comic books for children and two COVID-19 education videos for parents will increase COVID-19 testing and vaccine uptake in children.
Secondary Objectives:	
• To determine if implementing three COVID-19 education comics books for children and two COVID-19 education videos for parents will increase physical activity, improve sleep, increase emotional regulation in children.• To determine if implementing three COVID-19 education comics books for children and two COVID-19 education videos for parents will increase physical activity, improve sleep, decrease depression and anxiety in parents
Population:	Children ages 3-5 enrolled in the Early Learning program in Yakima School District
Study Size:	Early Learning is an ancillary study with no defined sample size. We will enroll and recruit participants for a total of eight weeks
Primary Outcome Measurements:	
A. COVID-19 testing data available through self-reported surveyB. COVID-19 vaccine data available through self-reported survey
Study Duration:	11 months – September 2022- August 2023

3. Study Design

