The ancillary study runs parallel with the larger ROSSEY RCT. Recruitment, enrollment, and baseline assessment are expected to last two months (September-November 2022). Enrolled participants will not receive the comic book and parent video series until after completion of the ROSSEY RCT Post 1 follow-up Survey to not bias the data of older siblings participating in the ROSSEY RCT. A follow-up assessment for Early Learning participants is anticipated to take place 10 months after the launch of recruitment (July-August 2023)

4. Sample size and power

Early Learning is an ancillary study of 50 participants. We will enroll and recruit participants for a total of eight weeks.

Enrollment Criteria

Parent/Guardian eligibility criteria for participation in the study include:

- Must have a child attending the Early Learning Program in the Yakima School District
- Must be able to provide informed consent and legal guardian assent either virtually, on the telephone, or in-person.
- Must have a permanent mailing address available for study staff to mail necessary materials OR a working email address.

5. Population and Data Source

Participants enrolled in the ROSSEY Study: 50 children and parents from the Yakima School District. Any participants subsequently found to be ineligible will be removed. The data sources for the primary analyses are COVID testing results received from the school administration and the survey data as entered in REDCap. The COVID vaccination status data is obtained through the parent and child surveys, completed in REDCap.

6. Presentation of analyses

For each of the continuous outcomes (including the primary outcome), the mean and standard deviation will be presented pre/post intervention and p value. For binary outcomes, the percentage and frequency of children in the outcome category of interest (e.g., percentage vaccinated) will be presented pre/post and p value.

7. Outcome Definitions

a. Primary Outcomes

The two co-primary outcomes of the trial are COVID-19 testing and COVID-19 vaccine uptake. COVID-19 data are captured through school testing and self-reported survey, and COVID-19 vaccine uptake data are captured through self-reported survey. All children and parent data will be included in the intention-to-treat analysis.

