COVID-19 testing: Health reports from the school are provided for the 2022-2023 school year that list positive covid test results of study participants with the date of testing and the school of attendance. Positive test results for COVID will be a binary, yes/no variable.

COVID-19 vaccine uptake: Parents are asked at enrollment to report their vaccination status and their child's vaccination status. At post survey, the parent is asked to report if they or their child have received any COVID-19 vaccine or booster since enrollment. Vaccination status will be a binary, yes/no variable.

b. Secondary Outcomes

Secondary outcomes for the trial include the following outcomes from the PROMIS – Pediatric and Parent Proxy Instruments. The PROMIS instruments used are Children's physical activity (PA), sleep, stress, depression, and anxiety. Parents' PA, sleep, stress, depression and anxiety. The final score is represented by the T-score, a standardized score with a mean of 50 and a standard deviation (SD) of 10.

The outcome measures will be collected at pre-and post-assessment.

8. Primary exposure definition

Receiving the educational materials: three comic books and two graphic motion videos.

9. Interim analysis plan

For this study, there was no interim analysis.

10. Multiple testing

We will adjust for multiple testing by controlling FDR.

11. Missing Data

We will inspect missing data mechanisms and the amount of missing data. We will conduct an additional sensitivity analysis with multiple imputations using multivariate imputation with chained equations (MICE) approach. We will report the amount of missing data and apply appropriate methods to account for the missing data.

12. Planned Statistical Analyses

a. Baseline Demographics

The baseline characteristics of enrolled participants will be summarized in a table.

b. Efficacy Analyses Overview

Pre/post-survey outcome analyses will be conducted after all participants have been contacted and the survey is closed with missing responses marked as loss to follow-up.

- 1) **Descriptive Analyses:** Positive COVID test results will be summarized by counts. Vaccine status and COVID testing results will be presented as counts and percentages. Continuous variables will be summarized by mean, standard deviation (SD), and median (IQR). Secondary outcomes will be compared using Chi-squared tests.

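### The testing co-primary captures change under the education plus free school testing, but the plan words it as an effect of the education

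*Protocol*

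**What the plan says.** - **Two offers at once.** After introducing the health education, Protocol I adds: "Simultaneously, free COVID-19 testing will be offered to families for their children at schools through the Yakima School District".
- **Recruitment rule.** Protocol III states: "We will recruit Early Learning students into the study regardless of their participation in SARS-CoV-2 testing provided by the Yakima School District". It then draws a consequence: "This will allow us to evaluate the effect of the risk communication strategies on the uptake of SARS-CoV-2 testing and other mitigation measures".
- **Design and question.** SAP 2 describes "a single-arm pre/post study". Its primary objective asks whether three comic books and "two COVID-19 education videos for parents will increase COVID-19 testing and vaccine uptake in children". Its central hypothesis is that "students and parents who view the risk communications will be more likely to have increased COVID-19 testing and vaccine uptake".
- **Outcome.** SAP 7a: "The two co-primary outcomes of the trial are COVID-19 testing and COVID-19 vaccine uptake".
- **Exposure.** SAP 8 gives the whole definition as: "Receiving the educational materials: three comic books and two graphic motion videos". Access to testing is not part of it.
- **Analysis.** SAP 12b(2) applies a chi-squared test at alpha 0.05 to vaccine uptake and testing and reports pre/post change. It names no covariate, time adjustment or comparison group. SAP 10 adds control of the false discovery rate (FDR) without listing which tests it covers.

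**The concern.** In a single-arm study, the only comparator is the same children at an earlier time. A change can be read as the effect of the materials only if everything else that moves the outcome stayed the same. For the testing co-primary, the protocol itself names something else that could move it: whether a child can get a free test at school. The plan does not record that access by period, hold it constant or allow for it in the conclusion.

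Protocol III appears to offer a safeguard, but it answers a different question. Enrolling children whether or not they use district testing keeps the sample from being selected on the outcome. It does nothing to separate two influences that act on the same children over the same months.

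What is at stake is the interpretation of one of two co-primaries. A rise caused by easier access could be reported as a benefit of the materials, and a fall caused by lost access could hide a real benefit. More participants would not help, because this is bias and not sampling error.

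**Working it through.** **Step 1. Is there a stated figure to reproduce?** No. Neither document gives a testing rate, an effect size or a power calculation. What follows is an illustration, and its rates are assumptions.

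**Step 2. What do the documents say about access in each period?**

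| Item | Where | What it implies for access |
|---|---|---|
| Baseline, September-November 2022 | Protocol I, SAP 3 | Start of a school year for children aged 3 to 5; some may be newly attending (assumption) |
| Children recruited whatever their use of district testing | Protocol III | Can be read as testing already in place at recruitment |
| Follow-up, July-August 2023 | Protocol I, SAP 3 | Access may be lower if school testing stops in summer (assumption) |
| Dates on which district testing was offered | Not given | Unknown |

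Access could therefore have been constant, risen or fallen. The documents do not settle which.

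**Step 3. How large could the consequence be?** Inputs:

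- n = 50 at each time (SAP 4 and 5; SAP 2 and Protocol IV define no sample size);
- alpha = 0.05 (SAP 12b(2)), taken as two-sided;
- no education effect (assumed);
- pre rate p1 = 20% and post rate p2, with the difference due to access alone (assumed);
- pre and post treated as independent samples, as the named test does.

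The bias is p2 - p1. The chance of a significant result is approximately

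Φ[(d - z × SE0) / SE1], where d = |p2 - p1|, p̄ = (p1 + p2)/2, SE0 = √(2p̄(1 - p̄)/n) and SE1 = √((p1(1 - p1) + p2(1 - p2))/n).

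- 20% to 30%: SE0 = √(2 × 0.25 × 0.75/50) = 0.0866; SE1 = √((0.16 + 0.21)/50) = 0.0860; (0.10 - 1.96 × 0.0866)/0.0860 = -0.81; probability 0.21.
- 20% to 40%: SE0 = √(2 × 0.30 × 0.70/50) = 0.0917; SE1 = √((0.16 + 0.24)/50) = 0.0894; (0.20 - 1.96 × 0.0917)/0.0894 = 0.23; probability 0.59.

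Exact enumeration of the two binomials with the uncorrected chi-squared test gives:

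| Pre to post, access only | Bias (points) | Significant at 0.05 |
|---|---|---|
| 20% to 20% | 0 | 5% |
| 20% to 30% | +10 | 21% |
| 20% to 40% | +20 | 60% |
| 20% to 10% | -10 | 30% |

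**Step 4. Does FDR control remove it?** With the two co-primaries as the family, the strictest step is 0.05 × 1/2 = 0.025. The 20-point rise is then significant in 48% of trials, against 60% at 0.05. The threshold lowers the rejection rate but leaves the 20-point bias as it is.

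**Step 5. Does a paired test remove it?** No. In 20,000 simulated trials of 50 children measured twice, exact McNemar rejected in 50% of trials (within-child latent correlation 0) and 66% (correlation 0.5) for the same 20% to 40% shift.

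**The case against.** The strongest reply is that nothing shows access changed. Protocol III speaks of district testing as something already provided, and Protocol V requires the child to be attending the program. On that reading, free school testing is the constant setting of the study and biases nothing. This stands. A reader might infer from the table that the trial will report a false effect of the materials, but the documents do not support that. They support only that constancy is assumed and not checked.

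Second, the shift sizes are invented, and SAP 10 controls the FDR. Both are true. The figures show sensitivity and are not a forecast. They also describe a generic yes/no testing variable, whereas SAP 7a codes a positive result.

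Third, the SAP never says in so many words that any change will be credited to the materials, and SAP 12b(2) promises only to report change over time. That is correct as regards SAP 12b(2). However, the SAP 2 objective and hypothesis, the SAP 8 exposure and the Protocol III sentence leave no other explanation on the page.

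Fourth, any single-arm pre/post study has this weakness, and matching access would still leave infection waves, policy changes and the children's age. This is true. The point still deserves its own line, because the protocol names this influence itself and then claims that a recruitment rule deals with it.

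Finally, it is tempting to ask for tests to be split by source and restricted to dates of equal access, using the school reports. The described data do not allow this. SAP 7a says that those reports list positive results with dates, and neither document describes a survey item for the date or place of a test.

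**Conclusion.** The concern holds as a point about attribution. The testing co-primary, as planned, estimates a pre/post change in a setting where free school testing was also on offer. The objective and Protocol III present it as the effect of the education, and recruiting regardless of testing participation does not justify that step.

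The size of any bias is unknown. It is zero if access was the same in both periods; otherwise it equals the access-driven change, in either direction. Under the assumed rates, 10- and 20-point rises from 20% give a significant result in 21% and 60% of trials with no education effect (48% for the 20-point rise at 0.025). These results rest on 50 children per period, independence between periods and a two-sided test. A reader should not take them as evidence that such shifts occurred.

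This is an inexpensive improvement that changes what may be concluded about a co-primary. It does not show that the planned result is wrong.

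**What to change.** 1. In SAP 2, SAP 12b(2) and Protocol III, state that the testing co-primary estimates the pre/post change under the education together with free school testing.
2. In Protocol III, remove the statement that recruiting regardless of testing participation allows the education's effect on testing to be evaluated. The recruitment rule itself can stay.
3. Obtain from the district the dates on which school testing was offered, and report whether it was available in each period.
4. Attempt comparisons restricted by source or date only if the surveys or district records turn out to hold test dates and places, including for negative tests.

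**Cost.** Items 1 and 2 are wording and need no new data. Item 3 is one request to the district. None needs new participants. The price is a narrower conclusion for this co-primary.

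**A separate matter to settle first.** Protocol I and SAP 3 place follow-up in July-August 2023, while Protocol VI ties distribution of the materials to December 2023 and follow-up to six weeks after distribution. The school reports in SAP 7a cover only the 2022-2023 school year. These passages must be reconciled before any post period, and so any access during it, can be defined.

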- 2) **Primary Objectives:** The primary analysis of vaccine uptake and COVID testing will be conducted using a chi-squared test using $\alpha = 0.05$ and report pre/post changes over time.
- 3) **Secondary outcomes:** The secondary outcomes for the trial include measures from the PROMIS – Pediatric and Parent Proxy Instruments. The PROMIS instruments used are children's PA, sleep, stress, depression, and anxiety and parents' PA, sleep, stress, depression, and anxiety.

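### The plan neither limits enrolment to one child per family nor says how a shared parent is entered, and its chi-squared test treats all records as independent, so its true size need not be 0.05

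*Protocol*

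**What the plan says.** - **Eligibility (Protocol V, repeated under SAP 4).** The parent or guardian "Must have a child attending the Early Learning Program in the Yakima School District". No maximum number of children, index child or household rule is stated.
- **Population (Protocol III).** The study will "recruit Early Learning students (3, 4 and 5 years old) and their parent or Guardian(s) into the research study". Three adjacent ages are covered, so siblings or twins could both qualify.
- **Enrolment (Protocol VI, Recruitment, Screening and Consent).** "Families will have two options to enroll children in the study". The sentence concerns the route of enrolment and its plural is generic, so it is weak evidence on how many children a family may enter.
- **Records analysed (SAP 7a).** "All children and parent data will be included in the intention-to-treat analysis". SAP 7 also has parents report their own vaccination and lists PROMIS measures for the parents themselves.
- **Primary test (SAP 12b, item 2).** "The primary analysis of vaccine uptake and COVID testing will be conducted using a chi-squared test", at alpha 0.05. No pairing, family term or robust variance is mentioned.
- **Number (SAP 4, SAP 5, Protocol IV).** SAP 4: "Early Learning is an ancillary study of 50 participants". SAP 5: "Participants enrolled in the ROSSEY Study: 50 children and parents from the Yakima School District". Protocol IV: "Early Learning is an ancillary study with no defined sample size". Whether 50 means parent-child pairs or people is not clear.

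**The concern.** An ordinary chi-squared test counts each record as a separate piece of information. Two children of one family probably share the decision to vaccinate or test. If the database holds one row per child, the answers of a parent with two enrolled children would appear twice. Nothing in the SAP defines the unit of analysis or prevents this.

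At stake are the true size of the two co-primary tests and the reported parent counts and percentages, which would be misstated if a parent entered twice. The same test also ignores that pre and post values come from the same people, so the two faults have to be assessed together.

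**Working it through.** **Inputs.** From the documents: 50 participants (SAP 4), taken here as 50 children; chi-squared test at 0.05 (SAP 12b), treated as two-sided; pre and post measurement (SAP 7). The 50 comes with no derivation, so there is no planning figure to reproduce. Assumed, because the documents give no values: number of sibling pairs k, within-family correlation ICC, correlation ρ between a child's pre and post values, and an outcome probability of 0.4 in the simulation.

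**Step 1: families alone (ρ = 0).** With k pairs among 50 children, the share of records with a sibling record is s = 2k/50. The variance is multiplied by 1 + s × ICC. True size = 2 × (1 − Φ(1.96/√ratio)). At ICC = 1:

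| k | s | Variance ratio | Effective n (50/ratio) | True size |
|---|---|---|---|---|
| 0 | 0 | 1.00 | 50 | 5.0% |
| 2 | 0.08 | 1.08 | 46 | 5.9% |
| 5 | 0.20 | 1.20 | 42 | 7.4% |
| 10 | 0.40 | 1.40 | 36 | 9.8% |

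With ICC = 0.5 and k = 5 the ratio is 1.10 and the size 6.2%.

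**Step 2: add the ignored pairing.** The true variance of the pre/post difference, divided by the variance that the unpaired test assumes, is (1 − ρ) × (1 + s × ICC). This takes the cross-time correlation between siblings as ICC × ρ. For k = 5 and ICC = 1, with ρ measured between the yes/no values:

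| ρ | Ratio | True size |
|---|---|---|
| 0 | 1.00 × 1.20 = 1.20 | 7.4% |
| 0.19 | 0.81 × 1.20 = 0.97 | 4.7% |
| 0.30 | 0.70 × 1.20 = 0.84 | 3.3% |
| 0.41 | 0.59 × 1.20 = 0.71 | 2.0% |
| 0.50 | 0.50 × 1.20 = 0.60 | 1.1% |

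The ratio exceeds 1 only when ρ < s × ICC/(1 + s × ICC) = 0.20/1.20 = 0.17. With s = 0.10 the limit is 0.10/1.10 = 0.09.

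**Step 3: simulation.** Settings: 50 children, 5 pairs with identical outcomes, probability 0.4 at both times, 40,000 runs. The pre/post correlation is set on an underlying normal scale; 0, 0.3 and 0.6 there correspond to about 0, 0.19 and 0.41 between the yes/no values, which links this table to Step 2.

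| Underlying correlation | Chi-squared as planned | McNemar, families ignored |
|---|---|---|
| 0 | 7.6% | 7.8% |
| 0.3 | 4.9% | 7.7% |
| 0.6 | 2.2% (2.1 to 2.2% in repeated runs) | 6.9% |

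The formula and the simulation agree to within about 0.3 percentage points.

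**Step 4: remedies.**
- One child per family, planned chi-squared test kept: at underlying correlation 0.3 the ratio falls to 0.81 and the size to about 2.8 to 2.9%, further from 5% than before.
- Within-child change with a variance built from family totals: the size was between 4.7% and 5.6% across the scenarios examined. In the runs above it was 5.2 to 5.3% with a t reference on families − 1 = 44 degrees of freedom, and 5.8 to 5.9% with a normal reference.

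**The case against.** A reader might infer that the p values come out too small and that type I error exceeds 0.05. The documents do not support that for the test as planned. Ignoring the pairing pushes p values up when ρ is positive, and a ρ above 0.17 on the yes/no scale outweighs 5 fully correlated pairs. This objection stands, and the direction has to be left open. It does not make the test sound: two errors that cancel by an unknown amount do not give a stated size. Nor is a sizeable ρ assured. SAP 7a sets vaccination status at enrolment against any dose since enrolment, and codes testing as a positive result, which is episodic.

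A reader might also infer that parents are in fact counted twice. The documents do not show this. They do not say that parent data are entered once per child or that any family enrolled two Early Learning children, and different guardians could answer for different children. The siblings in Protocol I and VI and in SAP 3 are those in the main RCT.

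Two further limits stand. The number of pairs is assumed; 10 pairs would mean 40% of children with an enrolled sibling, for which the documents give no support. And no size can be derived for the parent PROMIS T-scores, because SAP 12b item 3 names no test and item 1 mentions only chi-squared tests.

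**Conclusion.** The gap is real. Several children per family are allowed, the handling of a shared parent is unstated, and the planned test cannot account for either. If siblings enrol, the true size differs from 0.05 in a direction that the documents do not settle: from about 7.6% down to 2.2% over the correlations simulated, and down to 1.1% by formula at ρ = 0.5 on the yes/no scale. If the sponsor corrected only the pairing, the family effect would then show in full, at about 7 to 8%.

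These figures rest on an assumed 5 pairs among 50 children and within-family correlation 1. With fewer pairs or a lower correlation the family effect is smaller, and with no pairs it is nil, although the pairing fault would remain. Priority is low to moderate.

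**What to change.** In SAP 5, define the units: each parent enters the parent outcomes once, each child is linked to a household identifier, and the number of families is reported next to the number of children.

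In SAP 12b, replace the plain chi-squared test with a paired analysis of pre/post change whose standard errors are clustered by family. GEE with robust variance or a bootstrap by family would serve, and either handles siblings and repeated measures together. With about 45 to 50 families, name a small-sample reference such as t on families − 1 degrees of freedom. Taking one child per family is not enough alone, because it leaves the pairing fault and discards children.

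Cost: a few SAP sentences and a household ID in REDCap. Contact details are already collected, so families can probably be linked after enrolment. Intervals may widen slightly for outcomes shared within a family. If no siblings enrolled, a sentence saying so closes the family part of the point.
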